8.0 Trial Procedures

The study calendar - Section 10.0 summarizes the trial procedures to be performed at each visit. Individual trial procedures are described in detail below. It may be necessary to perform these procedures at unscheduled time points if deemed clinically necessary by the investigator.

Furthermore, additional evaluations/testing may be deemed necessary by the investigator for reasons related to subject safety.

8.1. Administrative Procedures

8.1.1. Informed Consent

The Investigator must obtain documented consent from each potential subject prior to participating in a clinical trial.

8.1.2. Inclusion/Exclusion Criteria

All inclusion and exclusion criteria will be reviewed by the investigator or qualified designee to ensure that the subject qualifies for the trial.

8.1.3. Medical History

A medical history will be obtained by the investigator or qualified designee. Medical history will include all active conditions, and any condition diagnosed within the prior 10 years that are considered to be clinically significant by the Investigator. Details regarding the disease for which the subject has enrolled in this study will be recorded separately and not listed as medical history.

8.1.4. Prior and Concomitant Medications Review

Prior Medications

The investigator or qualified designee will review prior medication use, including any protocol-specified washout requirement, and record prior medication taken by the subject within 28 days before starting the trial. Treatment for the disease for which the subject has enrolled in this study will be recorded separately and not listed as a prior medication.

Concomitant Medications

The investigator or qualified designee will record medication, if any, taken by the subject during the trial. All medications related to reportable SAEs and ECIs should be recorded as defined in Section 9.2.

8.1.5. Disease Details and Treatments

Disease Details

The investigator or qualified designee will obtain prior and current details regarding disease status.

8.1.6. Prior Treatment Details

The investigator or qualified designee will review all prior cancer treatments including systemic treatments, radiation and surgeries.

Subsequent Anti-Cancer Therapy Status

The investigator or qualified designee will review all new anti-neoplastic therapy initiated after the last dose of trial treatment. If a subject initiates a new anti-cancer therapy within 30 days after the last dose of trial treatment, the 30 day Safety Follow-up visit must occur before the first dose of the new therapy. Once new anti-cancer therapy has been initiated the subject will move into survival follow-up.

8.2. Clinical Procedures/Assessments

8.2.1. Adverse Event (AE) Monitoring

The investigator or qualified designee will assess each subject to evaluate for potential new or worsening AEs as specified in the Trial Flow Chart and more frequently if clinically indicated.

All AEs of unknown etiology associated with pembrolizumab exposure should be evaluated to determine if it is possibly an event of clinical interest (ECI) of a potentially immunologic etiology (irAE). See Section 6.4 regarding the identification, evaluation and management of AEs of a potential immunological etiology (also Appendix- section 17.3).

8.2.2. Physical Exam

The investigator or qualified designee will perform a complete physical exam during the screening period. Clinically significant abnormal findings should be recorded as medical history. A full physical exam should be performed during screening.

8.2.3. Vital Signs

The investigator or qualified designee will take vital signs at screening, prior to the administration of each dose of trial treatment and at treatment discontinuation as specified in the study calendar (Section 10.0). Vital signs should include temperature, pulse, respiratory rate, weight and blood pressure. Height will be measured at screening only.

8.2.4. Eastern Cooperative Oncology Group (ECOG) Performance Scale

The investigator or qualified designee will assess ECOG status (see Appendix- section 17.1) at screening, prior to the administration of each dose of trial treatment and discontinuation of trial treatment as specified in the Trial Flow Chart.

8.2.5. Tumor Imaging and Assessment of Disease

Scans will be performed at baseline, and every 9 weeks (\pm 7 days) while on treatment for the first year and every 12 weeks (\pm 7 days) thereafter. Imaging during follow up is outlined in section 8.5.3.

8.2.6. Tumor Tissue Collection and Correlative Studies Blood Sampling

For details in regards to tumor tissue collection please see Section 8.3.1 Tumor tissue processing, and shipment instructions are provided in the Appendix – section 17.2.

Peripheral blood samples will be collected immediately prior to the first dose of pembrolizumab (time 1), at cycle 3 (immediately prior to dose 3; time 2) and at time of progression (time 3) for correlative studies as outlined in Section 10.0 (study calendar).

Processing of blood samples will occur at FCCC as outlined in Appendix (section 17.2). Blood samples will be shipped to Protocol Support Laboratory (PSL) at Fox Chase as outlined in Appendix. Samples will be distributed from the PSL at Fox Chase to [name]'s lab. Remaining cells will be stored in the PSL

8.3. Laboratory Procedures/Assessments

Details regarding specific laboratory procedures/assessments to be performed in this trial are provided below.

Laboratory tests for hematology, chemistry, urinalysis, and others are specified in Table 4.

Hematology	Chemistry	Urinalysis	Other
Hematocrit	Albumin	Blood	Serum β-human chorionic gonadotropin†
Hemoglobin	Alkaline phosphatase	Glucose	(β-hCG)†
Platelet count	Alanine aminotransferase (ALT)	Protein	PT (INR)
WBC (total and differential)	Aspartate aminotransferase (AST)	Specific gravity	aPTT
Red Blood Cell Count	Total Bilirubin	Microscopic exam (If abnormal)	Total thriiodothyronine (T3)
Absolute Neutrophil Count	Carbon Dioxide	results are noted	Free tyroxine (T4)
Absolute Lymphocyte Count	$(CO_2 \text{ or biocarbonate})$		Thyroid stimulating hormone (TSH)
	Blood Urea Nitrogen		Lipase
	Calcium		HIV antibody
	Chloride		Blood for correlative studies
	Glucose		HepBsAg
	Potassium		HCV RNA
	Sodium		
	Direct Bilirubin (If total bilirubin is elevated above the upper limit of normal)		
	Total protein		
+ Perform on women of	childbearing potential only.		

Table 4. Laboratory Tests

Laboratory tests for screening will be performed within 10 days prior to the first dose of treatment. After Cycle 1, pre-dose laboratory procedures can be conducted up to 72 hours prior to dosing. Results must be reviewed by the investigator or qualified designee and found to be acceptable prior to each dose of trial treatment.

8.3.1. Biomarker Evaluations

Blood Collection for correlative studies/biomarkers

Sample collection, processing, storage, and shipment instructions for samples is provided in the Appendix (section 17.2).

Tumor tissue collection for correlative studies

Pathology samples from archived tumor biopsies (or optional fresh biopsy done before treatment initiation, if no archived tissue available) are to be submitted within 28 days of starting cycle 1. Representative FFPE tumor tissue blocks specimen are to be submitted to the Fox Chase Cancer Center PSL.

The following pathology material needs to be submitted:

- Paraffin embedded biopsy or cell block, and
- Any available pathology report related to that tumor sample

NOTE: If a block is unavailable for submission, slides are to be submitted. All slides must be adequately labeled, with slides numbered sequentially in the order cut. Alternative submission requirement:

- One (1) H&E slide, and
- Ten (10) 4 µm unstained air-dried on plus slides.

Shipment of pathology samples is outlined in the Appendix (section 17.2)

8.4. Other Procedures

8.4.1. Withdrawal/Discontinuation

When a subject discontinues/withdraws prior to trial completion, all applicable activities scheduled for the final trial visit should be performed at the time of discontinuation. Any adverse events which are present at the time of discontinuation/withdrawal should be followed in accordance with the safety requirements outlined in Section 9.2 - Assessing and Recording Adverse Events. Subjects who a) attain a CR or b) complete 35 cycles of treatment with pembrolizumab may discontinue treatment with the option of restarting treatment if they meet the criteria specified in Section 8.5.4. After discontinuing treatment following assessment of CR, these subjects should return to the site for a Safety Follow-up Visit (described in Section 8.5.3) and then proceed to the Follow-Up Period of the study.

8.5. Visit Requirements

Visit requirements are outlined in Section 10.0 – study calendar. Specific procedure-related details are provided above in Section 8.0 - Trial Procedures.

8.5.1. Screening Period

Subjects will be screened within 28 prior to protocol treatment. Study procedures and information regarding the nature of the study will be reviewed with potential subjects and written informed consent will be obtained prior to any study related procedures. Screening procedures are described in Section 10.0 - study calendar.

8.5.2. Treatment Period

Subjects will be treated every 3 weeks of Pembrolizumab for up to 35 cycles. During the treatment phase patients will be evaluated clinically before each dose of Pembrolizumab for toxicities and radiologically every 9 weeks for disease progression as outlined in detail in Section 10.0 -study calendar.

8.5.3. Post-Treatment Visits

Safety Follow-Up Visit

The mandatory Safety Follow-Up Visit should be conducted approximately 30 days after the last dose of trial treatment or before the initiation of a new anti-cancer treatment, whichever comes first. All AEs that occur prior to the 120 day Safety Follow-Up Visit should be recorded. Subjects with an AE of Grade > 1 will be followed until the resolution of the AE to Grade 0-1 or until the beginning of a new anti-neoplastic therapy, whichever occurs first. SAEs that occur within 120 days of the end of treatment or before initiation of a new anti-cancer treatment should also be followed and recorded. Subjects who are eligible for retreatment with pembrolizumab (as described in Section 8.5.4) may have up to two safety follow-up visits, one after the Treatment Period and one after the Second Course Phase.

Follow-up Visits

Subjects who discontinue trial treatment for a reason other than disease progression will move into the Follow-Up Phase and should be assessed every 9 weeks $(63 \pm 7 \text{ days})$ by radiologic imaging to monitor disease status. After 1 year, the imaging time point will occur every 12 weeks (\pm 7 days). Every effort should be made to collect information regarding disease status until the start of new anti-neoplastic therapy, disease progression, death, end of the study or if the subject begins retreatment with pembrolizumab as detailed in Section 8.5.4. Information regarding post-study anti-neoplastic treatment will be collected if new treatment is initiated.

Survival Follow-up

Once a subject experiences confirmed disease progression or starts a new anti-cancer therapy, the subject moves into the survival follow-up phase and should be contacted by telephone every 12 weeks to assess for survival status until death, withdrawal of consent, or the end of the study, whichever occurs first.

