6.6. Participant Withdrawal/Discontinuation Criteria

Participants may withdraw consent at any time for any reason or be dropped from the trial at the discretion of the investigator should any untoward effect occur. In addition, a participant may be withdrawn by the investigator if enrollment into the trial is inappropriate, the trial plan is violated, or for administrative and/or other safety reasons. Specific details regarding discontinuation or withdrawal are provided in section 8.4 – Other Procedures.

A participant must be discontinued from the trial for any of the following reasons:

- The subject or legal representative (such as a parent or legal guardian) withdraws consent.
- Disease progression (for definition see Section12)
- Unacceptable adverse experiences as described in Section 7.0
- Intercurrent illness that prevents further administration of treatment
- Investigator's decision to withdraw the subject
- The participant has a confirmed positive serum pregnancy test
- Noncompliance with trial treatment or procedure requirements
- The subject is lost to follow-up
- Completed 35 cycles of treatment with pembrolizumab

Note: Subjects who stop pembrolizumab after 35 cycles may be eligible for up to 18 cycles of additional study treatment if they progress after stopping study treatment provided they meet the requirements detailed in Section8.5.4.

• Administrative reasons

The End of Treatment and Follow-up visit procedures are listed in Section 10 (Study calendar) and Section 8.5 (Visit Requirements). After the end of treatment, each subject will be followed for 120 days for adverse event monitoring (events of clinical interest will be collected for 120 days after the end of treatment). Subjects who discontinue for reasons other than progressive disease will have post-treatment follow-up for disease status until disease progression, initiating a non-study cancer treatment, withdrawing consent or becoming lost to follow-up. After documented disease progression each subject will be followed by telephone for overall survival until death, withdrawal of consent, or the end of the study, whichever occurs first.

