8.5.5. Treatment Beyond Disease Progression

See section 6.8 for further details. The decision to continue study treatment after the 1st evidence of disease progression is at the Investigator's discretion based on the clinical status of the subject as described in table 5. Confirmatory imaging maybe performed as early as 28 days later; alternatively, the scan performed at the next scheduled time point (every 42 days \pm 7 days) may be used as confirmation. Subjects may receive study treatment while waiting for confirmation of PD if they are clinically stable as defined by the following criteria:

- Absence of signs and symptoms (including worsening of laboratory values) indicating
- disease progression
- No decline in ECOG performance status
- Absence of rapid progression of disease
- Absence of progressive tumor at critical anatomical sites (e.g., cord compression)
- Requiring urgent alternative medical intervention
- Subjects exhibiting toxicity from trial therapy requiring discontinuation of trial therapy as outlined in Section 6.4.and 7.0 may NOT continue to receive trial therapy.

	Clinically stable		Clinically unstable				
	Imaging	Treatment	Imaging	Treatment			
1 st radiologic evidence of PD	Repeat imaging at > 4 weeks at site to confirm PD	May continue study treatment at the Investigator's discretion while awaiting confirmatory scan by site	Repeat imaging at > 4 weeks to confirm PD per physician discretion only	Discontinue treatment			
Repeat scan confirms PD (no reduction in tumor burden from prior scan)	No additional imaging required	Discontinue treatment	No additional imaging required	NA			
Repeat scan confirms PD (reduction in tumor burden from prior scan)	Continue regularly scheduled imaging assessments	Continue study treatment after consultation with Sponsor Investigator	Continue regularly scheduled imaging assessments	May restart study treatment if condition has improved and/or clinically stable per Investigator and Sponsor Investigators's discretion			
Repeat scan shows SD, PR or CR	Continue regularly scheduled imaging assessments	Continue study treatment at the Investigator's discretion	Continue regularly scheduled imaging assessments	May restart study treatment if condition has improved and/or clinically stable per Investigator's discretion			

Table 5

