¹ In subjects who discontinue study therapy without documented disease progression, every effort should be made to continue monitoring their disease status by radiologic imaging every 9 weeks (63 ± 7 days) in the first year and every 12 weeks (84 ± 7 days) after year 1 until (1) the start of new anti-cancer treatment, (2) disease progression as assessed by the investigator/site radiologist, (3) death, or (4) the end of the study, whichever occurs first.

^m End of treatment procedures will be conducted at the time of treatment discontinuation or at the end of 35 cycles, whichever occurs sooner

ⁿ Optional blood collections in consenting patients for sera, plasma and red blood cells for future research. In consenting patients, blood will be drawn prior to cycle 1, every other assessment, and at the end of treatment for future research.

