10.2. Retreatment Phase (Second Course of Treatment)

Trial Period:	Screening	Treatment Cycles ^a				End of Treatment	Post-Treatment			
	Pre-Re-Tx									a
Treatment Cycle/Title:		1	2	3	Cycle 4 and beyond	Discon	Safety Follow-up	Safety Follow-up	Follow Up Visits ^b	Survival Follow-Up
Scheduling Window (Days):			± 3	± 3	± 3	At time of Discon	30 days post discon	120 days post discon		Every 12 weeks
Eligibility criteria	Х									

Copyright© 2016 Fox Chase Cancer Center® Clinical Trials Operations. All rights reserved.

Version Date 03/03/17

Trial Period:	Screening	Treatment Cycles ^a				End of Treatment	1 Ost-11 catilicat			
Treatment Cuale/Titler	Pre-Re-Tx				Cycle 4 and		Safety	Safety	Follow Up	Survival
Treatment Cycle/Title:		1	2	3	beyond	Discon	Follow-up	Follow-up	Visits ^b	Follow-Up
Scheduling Window (Days):			± 3	± 3	± 3	At time of Discon	30 days post discon	120 days post discon		Every 12 weeks
Prior and Concomitant Medication Review	Х	Х	Х	Х	Х	Х	Х			
Pembrolizumab Administration		Х	Х	Х	Х					
Post-study anticancer therapy status									Х	Х
Survival Status										Х
Review Adverse Events		Х	Х	Х	Х	Х	Х	Х		
Full Physical Examination	Х	Х	Х	Х	Х	Х	Х			
Vital Signs and Weight ⁱ	Х	Х	Х	Х	Х	Х	Х			
ECOG Performance Status	Х	Х	Х	Х	Х	Х	Х			
Pregnancy Test –Serum β-HCG	X^h									
PT/INR and aPTT	X ^g									
CBC with Differential	X ^g	Х	Х	Х	Х	Х	Х			
Comprehensive Serum Chemistry Panel ^j	X ^g	Х	Х	Х	Х	Х	Х			
HIV antibody	Х									
HepBsAg	Х			1		Ì				
HCV RNA	Х	1								
Urinalysis	X ^g									
T3, FT4 and TSH	X ^g		1	Xc			Х			
Tumor Imaging ^{d,}	Х			Xe		X ^f	1		X ^k	

a Treatment cycles are 3 weeks (21-days)

^b Patients should be assessed every 9 weeks (63 ± 7 days) for the first 1 year (or until disease progression) for disease status. After 1 year, patients should be assessed every 12 weeks (± 7 days). Once a subject experiences confirmed disease progression or starts a new anti-cancer therapy they move into survival follow-up

^c Check during treatment phase every 3 cycles (screening, cycle 3, 6, 9, 12, 15, 18, etc.)

^d Preferably a contrast-enhanced CT scan of chest/abdomen and pelvis done within 28 days of restarting treatment(If cannot receive contrast, can substitute for CT chest without contrast and MRI abdomen/pelvis with contrast). Subsequent imaging should be of the same modality as the imaging at baseline.

Trial Period:	Screening	Treatment Cycles ^a				End of Treatment	Post-Treatment			

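### Survival follow-up starts at documented progression in Section 6.6 but at confirmed progression in Section 8.5.3 and the study calendars, so patients who stop at a never-confirmed first PD may get no survival calls after day 120

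*Combined protocol and SAP*

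**What the plan says.** All references are to the combined protocol and SAP.

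- **Section 8.5.3, Survival Follow-up:** "Once a subject experiences confirmed disease progression or starts a new anti-cancer therapy, the subject moves into the survival follow-up phase", with calls every 12 weeks.
- **Calendar 10.2, footnote b:** "Once a subject experiences confirmed disease progression or starts a new anti-cancer therapy they move into survival follow-up". Footnote b of calendar 10.1 is broken in the available text, but its legible fragments carry the same condition, including the word *confirmed*.
- **Section 6.6:** "After documented disease progression each subject will be followed by telephone for overall survival until death, withdrawal of consent, or the end of the study". There is no confirmation condition.
- **Section 8.5.3, Follow-up Visits (imaging):** "Subjects who discontinue trial treatment for a reason other than disease progression will move into the Follow-Up Phase". Footnote l of calendar 10.1 is similar: "In subjects who discontinue study therapy without documented disease progression, every effort should be made to continue monitoring their disease status".
- **Section 8.5.5, Table 5:** a clinically unstable patient stops treatment at first PD, and the imaging instruction is "Repeat imaging at > 4 weeks to confirm PD per physician discretion only". The note after Table 5 describes confirmed radiographic progression as two scans at least 28 days apart that show PD.
- **Safety follow-up:** "The mandatory Safety Follow-Up Visit should be conducted approximately 30 days after the last dose of trial treatment", or earlier if new treatment starts. Section 6.6 follows every patient for 120 days for adverse events, and both calendars have a 120-day visit.

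**The concern.** *Documented* and *confirmed* are different conditions in this protocol. PD in Section 12.4 needs no second scan, so a first PD on imaging is documented; it becomes confirmed only with a repeat scan. The patients for whom the difference matters are those whom Table 5 takes off treatment because they are clinically unstable, and for whom a second scan is optional.

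Such patients can be expected to die sooner than the others. If their survival status is not collected after the safety period, they are censored because they are doing badly. Kaplan-Meier assumes that censoring carries no information about prognosis, so the OS curve would then be too high. Status that is not collected at the time may not be recoverable later.

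**Working it through.** **1. The plan's own figures.** The documents give no OS figure to reproduce. The only design figures concern response rate (Section 13.1): n = 21, reject at 3 or more responses. With P(X ≥ 3) = 1 − Σ C(21,x) pˣ(1−p)²¹⁻ˣ over x = 0, 1, 2:

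- p = 0.05 gives 0.0849 (plan: 8.5%)
- p = 0.20 gives 0.8213 (plan: 82.1%)

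Both reproduce, and neither depends on survival follow-up.

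**2. Tracing one patient.** Take a clinically unstable patient who stops at first PD, has no repeat scan and starts no new therapy.

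| Text | Condition for entry | Met? |
|---|---|---|
| 8.5.3, imaging Follow-Up Phase | stopped for a reason other than progression | No |
| 10.1, footnote l | stopped without documented progression | No |
| 8.5.3, survival follow-up | confirmed progression or new therapy | No |
| 10.1 and 10.2, footnote b | confirmed progression or new therapy | No |
| 6.6, telephone follow-up for OS | documented progression | Yes |
| 6.6, 8.5.3 and calendars, safety follow-up | any end of treatment | Yes, to day 120 |

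Only 6.6 provides survival contact after day 120.

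**3. Does 6.6 settle it in practice?** Its closing paragraph sends sites to Sections 10 and 8.5 for end-of-treatment and follow-up procedures. Those are the two places with the narrower trigger, and no text says which governs. Both calendars mark Survival Status only in the Survival Follow-Up column, not at the 30- or 120-day visit. Expedited SAE reporting (9.2.3) leaves out deaths from progression of the study cancer. Section 12.6 defines PFS, but no OS definition or censoring rule is given.

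**4. Possible size.** Every input here is an assumption; none is in the documents.

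*Set A.* Times are exponential. Median time to PD is 2 months. A share f stops unstable and unconfirmed, with median survival of 2.5 months after PD; the rest have 7 months. Contact with the share f ends 120 days after PD. Everyone is censored at 24 months. Kaplan-Meier medians from 200,000 simulated patients:

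| f | True median | Estimated median | Shift |
|---|---|---|---|
| 20% | 8.84 | 9.19 | +0.35 |
| 40% | 7.72 | 8.19 | +0.47 |

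An independent run agreed to within 0.04 months for each median.

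In a trial of 21, these shares are 0.20 × 21 = 4.2 and 0.40 × 21 = 8.4 patients. With 120 days = 3.94 months, the fraction still alive at day 120 is 2^(−3.94/2.5) = 0.335, so about 1.4 to 2.8 patients would be censored alive.

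*Set B.* The other patients have median OS of 9 months. A share of 10 to 40% has PD at 2.1 months, then median survival of 1.5, 3 or 6 months, with contact to 4 months after PD. The shift runs from 0 to +0.50 months:

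- 40% and 1.5 months: 5.19 to 5.19. The median falls before censoring begins at 2.1 + 4 = 6.1 months.
- 10% and 3 months: 8.30 to 8.55
- 40% and 6 months: 8.53 to 9.03

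**5. If 6.6 is followed,** these patients stay under observation and the shift from this source is zero.

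**The case against.** The strongest reply is that the protocol already covers these patients. Section 6.6 applies to each subject and has no confirmation condition. Nothing ranks 8.5.3 above it, and 8.5.3 nowhere says that patients with unconfirmed PD go unfollowed. Section 5.1 also plans OS assessment every 12 weeks in long-term follow-up without mentioning confirmation. On this view the problem is one of wording.

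Much of that stands. A reader might infer that these patients belong to no follow-up phase and that OS is therefore overstated. The documents do not support either statement: 6.6 follows them for survival, and bias needs sites to apply 8.5.3 and the calendars instead, and the analysis to censor at last contact. A reader might also infer a larger bias by supposing that contact ends at the 30-day visit. Section 6.6 and both calendars take every patient to day 120, so that case is not the protocol's.

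The size is also modest beside sampling error. For an assumed exponential OS with a 9-month median and 21 uncensored patients, the standard error of the median is 1/(λ√n) = (9/ln 2)/√21 = 2.8 months.

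What the reply does not remove is the conflict itself. Section 6.6 delegates procedures to the sections that contradict it, and a site working from the calendar would find no survival call for such a patient.

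**Conclusion.** The point holds as an internal inconsistency with a possible effect on a secondary endpoint. Sections 6.6 and 8.5.3 and footnote b of both calendars give different triggers, and the difference falls on patients who stop at a first PD that is never confirmed and who start no new therapy.

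If sites follow 8.5.3 and the calendars, median OS may be biased upward, by about 0.4 to 0.5 months under Set A and by 0 to 0.5 months under Set B. The documents give neither the share of such patients nor their survival, so these are illustrations and not estimates. If sites follow 6.6, there is no bias from this source. No hypothesis or sample size rests on OS, and the response-rate test (8.5% level, 82.1% power) is untouched. The correction is worth making because it is nearly free and protects data that may not be recoverable.

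**What to change.** Reconcile 8.5.3 and footnote b of calendars 10.1 and 10.2 with 6.6 by stating that:

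1. every patient who has permanently stopped study treatment and has documented progression, confirmed or not, or who starts new anti-cancer therapy, enters 12-weekly survival follow-up;
2. every other patient off treatment enters the imaging Follow-Up Phase;
3. patients still on treatment after a first unconfirmed PD, as 6.8 and Table 5 allow, stay on the treatment calendar.

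The limit to patients off treatment is needed. Simply replacing *confirmed* with *documented* would move clinically stable patients into telephone follow-up while they were still receiving drug. No treatment rule changes.

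Cost: wording in three places, and a few telephone calls that 6.6 already requires.
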